3 BACKGROUND AND RATIONALE

3.1 Hypothesis

Combined treatment with eltrombopag (EP) and lenalidomide (CC-5013;REVLIMID) will reduce the incidence of thrombocytopenia due to Lenalidomide and enable patients to tolerate duration of therapy leading to higher rates of response.

3.2 Treatment of Thrombocytopenia in MDS or sAML/MDS

In a review of patients with MDS referred to the M. D. Anderson Cancer Center, the incidence of life-threatening thrombocytopenia was 16-40% depending on the MDS risk status, with a median survival of only 6 to 12 months. The incidence of thrombocytopenia increases with disease progression, and without effective therapies, some patients may experience life-threatening bleeding(1)

In MDS, the disease clone includes the megakaryocytic lineage. Megakaryocytes from patients with MDS show impaired proliferation and differentiation, thus causing thrombocytopenia (2). Additional aspects potentially contributing to thrombocytopenia in MDS are premature cell death of megakaryocytes and decreased platelet life span(3). Interestingly, these aspects can be observed in both patients with MDS, and patients with Idiopathic Thrombocytopenic Purpura (ITP). In MDS, the megakaryocytic proliferation is unresponsive to recombinant thrombopoietin (TPO), possibly due to deregulated TPO-receptor-mediated signaling(4) . In addition to the qualitative disturbance of the TPO-receptor, there is also a quantitative disturbance in terms of the number of TPO receptors, which show a reduced expression by 50% on MDS platelets, as well as on CD41+ and CD34+ cells as compared to normal cells. However, an in vitro study showed that CD61+ cells in suspension cultures increased with PEG-rHuMGDF (pegylated recombinant human MGDF)alone in 31 out of 39 patient samples from MDS patients (5). The clinical development of PEG-rHuMGDF was aborted owing to the development of cross-reacting autoantibodies against endogenous TPO. More recently, Phase II data were presented for another TPO-R agonist, romiplostim, which showed efficacy in 41% of the patients with low- or intermediate-1 risk MDS (6) However, few patients showed some direct or indirect evidence for disease progression [FDA Oncology Drug Advisory Committee Meeting, March 2008].

3.3 Treatment of Thrombocytopenia in MDS or sAML/MDS with Eltrombopag

Eltrombopag is an orally available, non-peptide TPO-receptor (TPO-R) agonist that stimulates platelet production by a mechanism similar, but not identical to endogenous TPO. Eltrombopag has been investigated at dose ranges of up to 200 mg daily for 5 days in healthy volunteers, and a dose-platelet response relationship was observed. In ITP, patients received up to 75 mg daily, and response rates were 28% with 30 mg, 67% with 50 mg, and 86% with 75 mg (response defined as a platelet count >50 Gi/L; the studied patients had platelet counts <30 Gi/L). The safety profile was similar to placebo (7). The positive results with eltrombopag in ITP are encouraging but the required dose and response in MDS are unknown. A phase I/II study in high risk MDS is presently evaluating the efficacy of eltrombopag at different doses with dose escalations of up to 300 mg.

It is theoretically possible that eltrombopag could worsen the disease in patients with MDS. However, in vitro preclinical studies in leukemia and lymphoma cell lines indicate that eltrombopag does not stimulate leukemia cell growth. In contrast to TPO, it may in fact suppress leukemic cell growth, as evidenced by the fact that 12 out of 14 leukemic/lymphoid cell lines tested demonstrated decreased proliferation when treated with eltrombopag, with an IC₅₀ of 0.5 to 15 µg/mL. This effect occurs even in the presence hematopoietic cytokines. (8-11). There is additional evidence from an ex vivo study indicating that eltrombopag does not stimulate leukemic cell growth. In 7 out of 7 BM specimens taken from patients with MDS or AML secondary to MDS, no increase in proliferation due to co-incubation with eltrombopag was seen (12).

3.4 Lenalidomide can result in transfusion independence in MDS but leads to a high rate of thrombocytopenia

Ineffective erythropoiesis remains the hallmark of myelodysplastic syndromes (MDS) for which few treatments offer sustained erythropoietic improvement (13). Lenalidomide (CC-5013; REVLIMID[®]) is an oral 4-amino glutarimide derivative of thalidomide that lacks the neurological toxicities of the parent compound. In a safety and efficacy study (MDS-001) investigating erythroid response to CC-5013 (lenalidomide) monotherapy in 43 patients with MDS, CC-5013 (lenalidomide) yielded a high frequency of major erythroid response (MER) in patients that had either failed prior treatment with erythropoietin or had high endogenous levels and high transfusion burden (14). Patients received treatment with one of three CC-5013 (lenalidomide) dose schedules, 25 or 10 mg daily, or 10 mg/day x 21 days every 4 weeks. Neutropenia (67%) and thrombocytopenia (57%) > grade 3 NCI-CTC version 2.0 were dose limiting, necessitating treatment interruption and dose-reduction in 25 (61%) patients. Other adverse effects were infrequent and of mild to moderate severity including pruritus, fatigue, diarrhea, edema, thyroid dysfunction and joint discomfort. Among the 36 patients completing more than one cycle of treatment, 24 (67%) experienced an erythroid response according to International Working Group (IWG) criteria. MER defined by sustained transfusion-independence (> 8 weeks) or a rise in hemoglobin >2 g/dl was achieved in 21 patients and 3 patients experienced a >50% reduction in red blood cell

(RBC) transfusions. Response rate was highest among evaluable patients with a chromosome 5q31.1 deletion (91%) compared to those with a normal karyotype (68%) or other chromosome abnormality (17%) [$P=0.009$], and response rate was higher in patients with lower (Low-/Intermediate-1) International Prognostic Scoring System (IPSS) risk categories (72% vs. 25%) [$P=0.098$] (15). Eleven of 17 (65%) patients with karyotypic abnormalities had a 50% or greater reduction in abnormal metaphases, including ten (57%) complete cytogenetic remissions. After a median follow-up of 109 weeks in November 2004, median duration of transfusion-independence had not been reached (81+; range, 19 to >128 weeks) with a median sustained hemoglobin (Hgb) of 13.4 g/dL (range, 11.5-15.8 g/dL) and median Hgb rise of 5.6 g/dL. The results of this study indicate that CC-5013 (lenalidomide) has significant and sustained erythropoietic and cytogenetic remitting activity in patients with Low/Intermediate-1 IPSS risk MDS that have failed or are unlikely to benefit from conventional cytokine therapy. Two phase II multicenter trials were completed in the past year, evaluating the frequency of MER to lenalidomide in patients with transfusion-dependent Low/Int-1 risk MDS with (MDS-003; N=148) or without a chromosome 5q31.1 deletion (MDS-002; N=215). Intent-to-treat analysis of the data confirm the high response rate in patients with del 5q31.1 (MER 66%, MER + Minor erythroid response 75%, cytogenetic response 70%) compared to a MER rate of 27% and Minor + MER rate of 44% in the MDS-002 results (15, 16). Grade 3 or greater neutropenia or thrombocytopenia were the principal reasons for treatment interruption and dose-reduction.

3.5 Rationale for combining lenalidomide and eltrombopag:

The rationale for combination is based on the following:

1. A major reason why lenalidomide cannot be used in MDS is because of the occurrence of thrombocytopenia. The use of EP will potentially raise platelet counts in these patients.
2. Thrombocytopenia in the first 2 months after Len therapy predicts the subsequent response to lenalidomide treatment in patients with low risk MDS (17) Thus raising platelet counts to enable continuation of lenalidomide therapy is important in these patients.
3. An increase in blasts has been a potential concern with the use of thrombopoietin mimetics and has been reported in a study with romiplostim (6) Preclinical studies have indicated that eltrombopag is less likely to increase blasts thus making it a possible potential therapeutic candidate in low risk MDS (12).

4 STUDY OBJECTIVES AND ENDPOINTS

4.1 Objectives

4.1.1 Primary Objectives

- To evaluate the rate of hematologic improvement of the eltrombopag/lenalidomide combination (as per Modified IWG criteria)
- To evaluate the safety and tolerability of the combination

4.1.2 Secondary Objectives

- To compare the time to hematologic improvement
- To evaluate the duration of hematologic improvement
- To evaluate the effect of combination treatment on platelet counts, platelet transfusions and bleeding events.
- To evaluate the frequency of bone marrow response (CR+PR) and cytogenetic response.
- To evaluate the relationship between mutations in bone marrow stem cells and response
- To evaluate the relationship between various stem and progenitor alterations and response

5 INVESTIGATIONAL PLAN

5.1 Overall design

This is a multicenter, Phase II study evaluating the efficacy and safety of the combination of lenalidomide and eltrombopag in low risk MDS. This study will include patients with low risk MDS (IPSS low and Int-1) with symptomatic anemia or transfusion dependence. Patients will be treated in 2 separate arms based on their baseline platelet counts:

Arm A : Patients with platelet counts $\geq 50k$ at baseline:

These patients will start Len at 10mg/d for 3 weeks/month, and will not start Eltrombopag until the platelet counts drop below 50,000. If platelets drop less than 50,000, Len will be stopped and Eltrombopag will be started at a dose of 100mg initially and titrated up (similar schema to 509 study) to achieve a platelet count above 50,000. Once the platelet count above 50,000 is achieved, the same dose of Eltrombopag will be continued for an additional two weeks. Once a platelet count $> 50,000$ is maintained for two weeks, Eltrombopag will be discontinued and Len will be started as a single agent. If the plts again fall below 50k then Len will be stopped and Eltrombopag will be re-initiated at the dose that was last given to the patient. Once the platelets are increased to above 50,000 and maintained at this level for 2 weeks, Len will be started again and this time will be given concurrently with Eltrombopag. These agents will now be used concurrently for all subsequent cycles.

Arm B: Patients with Plts $< 50k$ at baseline

These patients will not receive Len initially. Eltrombopag will be started alone at a dose of 100mg initially and titrated up (similar schema to 509 study) to achieve a

platelet count above 50,000. Once the platelet count above 50,000 is achieved, the same dose of eltrombopag will be continued to additional two weeks. Once the plt count > 50,000 is maintained for two weeks, the patients will discontinue eltrombopag and follow the treatment algorithm described for patients in arm A. Patients that never drop their platelet counts below 50,000 will not receive any additional eltrombopag. (Figure 1)

Treatment with myeloid growth factors is permitted for the management of neutropenia at the discretion of the treating investigator.

Study drugs will be continued until disease progression or unacceptable toxicities.

Bone marrow examinations will be performed at baseline, at every 4 months and at study discontinuation.

52 evaluable adult subjects with MDS will be evaluated.

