
STUDY DESIGN:
 
This is a multicenter, phase II study evaluating the efficacy and safety of the combination of lenalidomide and eltrombopag in low risk MDS.
	

Patients will be treated based on their baseline platelet counts:

Arm A: Patients with platelet counts $\geq 50k$ at baseline:

These patients will start Len at 10mg/d for 3 weeks/month, and will not start eltrombopag until the platelet counts drop below 50,000. If platelets drop less than 50,000, Len will be stopped and eltrombopag will be started at a dose of 100mg initially (50 mg for subjects of East Asian heritage) and titrated up to a maximum dose of 300 mg (150 mg for subjects of East Asian heritage) to achieve a platelet count above 50,000/L. Once a platelet count above 50,000 is achieved, the same dose of eltrombopag will be continued for an additional two weeks. Once a platelet count $> 50,000$ is maintained for two weeks, eltrombopag will be discontinued and Len will be started as a single agent. If the platelets again fall below 50,000 then Len will be stopped and eltrombopag will be re-initiated at the dose that was last given to the patient. Once the platelets are increased to above 50,000 and maintained at this level for 2 weeks, Len will be started again and this time will be given concurrently with eltrombopag. These agents will subsequently be used concurrently for all subsequent cycles.

Arm B: Patients with Plts $< 50k$ at baseline

These patients will not receive Len initially. Eltrombopag will be started alone at a dose of 100mg initially and titrated up (Table 4) to achieve a platelet count above 50,000. Once the platelet count above 50,000 is achieved, the same dose of eltrombopag will be continued for an additional two weeks. Once the plt count $> 50,000$ is maintained for two weeks, the patients will discontinue eltrombopag and follow the treatment algorithm described for patients in arm A.

[figure not shown]

Figure 1: Schema of the study (* starting dose of Eltrombopag for Asian subjects is 50mg)

STUDY ENDPOINTS

Primary:

Hematologic improvement

Secondary: Time to attain and duration of hematologic improvement Bone marrow morphologic and cytogenetic response Platelet counts and Bleeding events
	

STUDY DURATION:2 years
	
TOTAL SAMPLE SIZE:52patients

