Endocrine	Hyperthyroidism or hypothyroidism	
 Interrupt CC-5013 (lenalidomide) and initiate appropriate medical therapy. Resume CC-5013 (lenalidomide) at investigator's discretion (maintain dose level).
Cardiac Arrhythmias	Sinus bradycardia/other cardiac arrhythmia Grade 2	
 Hold (interrupt) dose. Follow at least weekly. If the toxicity resolves to \leq grade 1 resume at next lower dose level.
	\geq Grade 3	
 Discontinue CC-5013 (lenalidomide) study drug.
Other Toxicity	Other non-hematologic toxicity assessed as CC-5013 (lenalidomide)-related \geq Grade 3	
 Hold (interrupt) dose. Follow at least weekly. If the toxicity resolves to \leq grade 2 resume at next lower dose level.

[figure not shown]
Dosing for Eltrombopag

Patients will initially be started on 100 mg eltrombopag (50 mg for subjects of East Asian heritage). Thereafter, dependent on the platelet response (see Table 3 below), the dose of study medication can be increased every 2 weeks, up to a maximum dose of 300 mg/day (150 mg/day for subjects of East Asian heritage).

Modified dosing for subjects of East Asian heritage (i.e., Japanese, Chinese, Taiwanese and Korean) has been implemented for the following reasons. In healthy Japanese subjects, plasma eltrombopag AUC(0- τ) was approximately 80% higher when compared to non-Japanese healthy subjects who were predominantly Caucasian. Similarly, in patients with ITP, plasma eltrombopag exposure was approximately 70% higher in East Asian (i.e., Japanese, Chinese, Taiwanese and Korean) subjects as compared to non-East Asian subjects who were predominantly Caucasian.

Intra-individual dose adjustments will be made in a stepwise fashion, by sequentially increasing to dose levels of 100 mg, 200 mg or 300 mg as needed (50, 100, 150 mg for subjects of East Asian heritage). Titration of study medication with different dosages on different days will be permitted where needed in order to maintain a stable platelet count in the safe range without exceeding platelet counts >400 Gi/L. The dosing regimen of eltrombopag must be individualized based on platelet counts. Use the lowest effective dosing regimen to maintain platelet response.

Figure 4: Schema of dose adjustments for eltrombopag

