Eltrombopag must be taken either in a fasted state (i.e., 1 hour before or 2 hours after food) or taken with food low in calcium (no dairy products). There must be at least a 4-hour interval between eltrombopag and other medications, food, or supplements containing polyvalent cations such as iron, calcium, aluminum, magnesium, selenium, and zinc, including dairy products. After any eltrombopag dose adjustment, monitor platelet counts at least weekly for 2-3 weeks.

At eltrombopag dose levels 200 mg and above, subjects who have discontinued other drugs known to prolong QT and who still have a QTc >480 msec will be excluded

Table 2: Guidelines for Eltrombopag Dose Adjustments

Platelet Counts	Dose Adjustments
No platelet response	
Increase daily dose to the next dose level
 
If platelet counts do not stabilize at desired levels, consider dosing regimens such as different dose levels on alternating days.
 
Wait for 2 weeks to see the effect of the dose increase on platelet response before another dose increase is considered.

200-400 k/uL	
If no post-baseline BM examination has been performed:
 
Decrease daily dose considering dosing regimens such as different dose levels on alternating days.
 
If platelet counts remain between 200-400 k/uL, wait for 2 weeks to see the effect of the dose decrease on platelet response before another dose decrease is considered.

	
If BM blasts have decreased:
 
Maintain dose level and monitor platelet counts weekly.

	
If BM blasts have increased:
 
Decrease daily dose considering dosing regimens such as different dose levels on alternating days.
 
If platelet counts remain between 200-400 k/uL, wait for 2 weeks to see the effect of the dose decrease on platelet response before another dose decrease is considered

>400k/uL	Interrupt treatment and monitor platelets twice a week until platelet counts fall below 150 k/uL and restart treatment by reducing the daily dose to the next dose level considering dosing regimens such as different dose levels on alternating days.
----------	---

During eltrombopag therapy, CBCs, including platelet count and peripheral blood smears, should be assessed weekly until a stable platelet count has been achieved. CBCs including platelet counts and peripheral blood smears, should be obtained monthly thereafter. Blasts will be monitored as indicated in flowchart:

Algorithm for Blast Count Monitoring

[figure not shown]

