develops new or worsening morphological abnormalities or cytopenia, treatment with eltrombopag should be discontinued and a bone marrow biopsy, including staining for fibrosis considered.

Recurrence of Thrombocytopenia After Cessation of Eltrombopag

Discontinuation of eltrombopag may result in recurrence of thrombocytopenia. This recurrence of thrombocytopenia may increase the patient's risk of bleeding, particularly if eltrombopag is discontinued while the patient is on anticoagulants or antiplatelet agents. In the 3 controlled ITP clinical studies, transient decreases in platelet counts to levels lower than baseline were observed following discontinuation of treatment in 8% and 8% of the eltrombopag and placebo groups, respectively. Serious hemorrhagic events requiring the use of supportive ITP medications occurred in 4 severely thrombocytopenic patients within one month following the discontinuation of eltrombopag; none were reported among patients in the placebo group.

Following discontinuation of eltrombopag, weekly CBCs, including platelet counts for at least 4 weeks should be obtained and alternative treatments for recurrence of thrombocytopenia, according to current treatment guidelines, considered.

Thrombotic/thromboembolic complications

Eltrombopag may increase the risk of thrombotic/thromboembolic events.. Excessive doses of eltrombopag may increase platelet counts to a level that produces thrombotic/thromboembolic complications.

In the 3 controlled ITP clinical studies, thrombotic/thromboembolic complications occurred in four patients in the groups that received eltrombopag and none in the placebo groups. Thrombotic/thromboembolic complications have also been reported in the ITP extension study. The thrombotic/thromboembolic complications in patients with chronic ITP included both venous and arterial events and were observed at low and normal platelet counts.

Use caution when administering eltrombopag to patients with known risk factors for thromboembolism (e.g., Factor V Leiden, ATIII deficiency, antiphospholipid syndrome, chronic liver disease). To minimize the risk for thrombotic/thromboembolic complications, do not use eltrombopag in an attempt to normalize platelet counts. Follow the dose adjustment guidelines to achieve and maintain a platelet count of $\geq 50 \times 10^9/L$ as necessary to decrease the risk for bleeding

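### For a patient on eltrombopag alone, section 5.1 and Table 2 give incompatible dose instructions once platelets reach 200 k/µL, and again on restart after an interruption

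*Combined protocol and SAP*

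**What the plan says.** **Treatment algorithm.** Section 5.1 titrates eltrombopag up until platelets exceed 50,000. From then on "the same dose of Eltrombopag will be continued for an additional two weeks". The synopsis (Study Design) has the same instruction: "the same dose of eltrombopag will be continued for an additional two weeks". Neither names an upper count at which it ceases to apply. When the count has stayed above 50,000 for two weeks, "Eltrombopag will be discontinued and Len will be started as a single agent". The thrombocytopenia paragraph of section 8.1.2 repeats this stop without exception. If platelets fall again and recover, both drugs are given: "These agents will now be used concurrently for all subsequent cycles".

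**Count-based table.** Section 8.1.2 captions its eltrombopag guidelines as Table 2. With no platelet response, the dose goes up. At 200-400 k/µL it goes down if no post-baseline marrow has been examined or if blasts have increased. If blasts have decreased, the entry is "Maintain dose level and monitor platelet counts weekly". Above 400 k/µL it is "Interrupt treatment and monitor platelets twice a week until platelet counts fall below 150 k/uL and restart treatment", with the restart at a reduced dose. The table does not say which treatment phase it covers.

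**Starting dose.** Section 5.1 (both arms) and the synopsis Arm B text give 100 mg with no exception. Synopsis Arm A, the synopsis dosing box and the eltrombopag dosing text of section 8.1.2 give 50 mg for East Asian patients. The Figure 1 footnote gives 50 mg for Asian patients.

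**The concern.** A site that follows section 5.1 and a site that follows Table 2 can do different things with the same patient on the same day: one continues the dose while the other lowers it or interrupts the drug. No readable sentence says which text takes precedence. The trial is multicenter and safety is a primary objective. Eltrombopag exposure at high platelet counts should therefore follow from the protocol and not from the page a site consults. Section 9.2 itself names thrombosis as a risk when excessive doses raise platelet counts.

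The starting-dose statements have the same weakness. Read alone, section 5.1 gives an East Asian patient a different starting dose from the one in section 8.1.2.

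**Working it through.** The plan states no figure on this point, so there is none to reproduce. The check sets the texts side by side for a patient on eltrombopag alone, lenalidomide on hold, in the first eltrombopag course.

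| Platelet count | Section 5.1, synopsis, stop rule in 8.1.2 | Table 2 | Conflict? |
|---|---|---|---|
| Below 50 k/µL | Titrate up | Increase if no response | No |
| Above 50 and below 200 k/µL, no prior interruption | Same dose for two weeks, then stop | No row | No |
| 200-400 k/µL, no post-baseline marrow or blasts increased | Same dose for two weeks | Decrease | **Yes** |
| 200-400 k/µL, blasts decreased | Same dose for two weeks, then stop | Maintain | Not within the two weeks; at their end one text stops and the other maintains |
| Above 400 k/µL | Same dose for two weeks | Interrupt | **Yes** |
| Interrupted, now below 150 k/µL, above 50,000 for two weeks | Eltrombopag off, lenalidomide alone | Restart eltrombopag at a reduced dose | **Yes** |

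**Later phases.** After a second fall, section 5.1 re-initiates eltrombopag and, on recovery, gives both drugs. It does not repeat the same-dose instruction for that second course and does not stop eltrombopag at its end. The explicit clash therefore sits in the first course. In the concurrent phase section 5.1 fixes no eltrombopag dose, so Table 2 can apply unopposed.

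**Do the cross-references settle precedence?** No.
- Synopsis Arm B refers titration to Table 4, and no table with that caption appears in the readable text.
- The eltrombopag dosing text of section 8.1.2 refers to Table 3, but the caption Table 3 belongs to the event-reporting table in section 10.3.1.
- The guidelines themselves are captioned Table 2, a number that section 8.1.2 also cites for lenalidomide adverse events.
- Section 5.1 refers titration to the schema of another study, which it does not describe.

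**Starting dose.** The two statements differ by 100 mg / 50 mg = 2-fold. Two places lack the exception (section 5.1 and synopsis Arm B) and four carry it (synopsis Arm A, the Figure 1 footnote, the synopsis dosing box and section 8.1.2). The footnote's group, Asian, is also wider than the East Asian group named in the other three.

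**The case against.** The strongest reply is that the texts can be harmonised. Section 5.1 is an overview and section 8.1.2 is the operative dosing section. The latter requires dosing to be individualised by platelet count and aims to keep counts from exceeding 400 Gi/L. On that reading, keeping the same dose means only that it is not escalated further, and Table 2 is a safety overlay. This is plausible, and may be what was intended. But no readable sentence makes section 5.1 subject to Table 2, and the stop rule inside section 8.1.2 carries no exception, so the restart conflict lies within the operative section itself. Figures 1, 4 and 5 (study schema, eltrombopag adjustment, blast monitoring) could not be read and may clarify the intent. Even so, the written instructions would still disagree.

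The reply is right that the conflict is narrow and that the 50 mg exception is already in several places, including a footnote to a figure that section 5.1 cites.

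Some stronger readings are tempting, but the documents do not support them:
- *That the thromboses in the chronic liver disease study (section 9.2) measure the risk here.* All those in the eltrombopag group were in the portal venous system, in patients with liver disease. This trial excludes documented cirrhosis, known splenic vein thrombosis and patients judged at increased thrombotic risk. Lenalidomide is also on hold in the disputed two weeks.
- *That the conflict moves the lenalidomide start date.* The trigger is a count above 50,000 for two weeks, and Table 2 says nothing about lenalidomide.
- *That restarting below 150 k/µL overshoots a target of 50,000.* The protocol uses 50,000 as a floor.
- *That maintaining the dose at 200-400 k/µL when blasts have decreased contradicts "Use the lowest effective dosing regimen to maintain platelet response" and "do not use eltrombopag in an attempt to normalize platelet counts".* The table entry is a specific conditional trial rule. The second statement comes from a section that summarises prescribing information, largely from another indication.

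**Conclusion.** The protocol is inconsistent as written, within a limited range. In the eltrombopag-alone phase, the same-dose-then-stop rule and Table 2 cannot both be followed in two situations:

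1. The count is 200-400 k/µL within the two weeks, with no post-baseline marrow or with increased blasts, or it is above 400 k/µL.
2. A patient interrupted under Table 2 is below 150 k/µL but has been above 50,000 for two weeks.

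A reader might infer that the algorithm and the table disagree throughout. They do not: there is no other conflict at 50-200 k/µL, and none in the concurrent phase.

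The number of patients affected cannot be estimated. The documents do not say how often 200 k/µL is reached, and section 3.3 describes the required dose and response in MDS as unknown. The conclusion assumes that Table 2 applies in every phase, because nothing restricts it, and that the unread figures contain no rule of precedence.

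The starting-dose discrepancy is a separate, smaller inconsistency of 2-fold between statements. Both points bear on patient safety, and both need the passages reconciled. Which rule or dose is right is a clinical choice for the sponsor.

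**What to change.** - Reconcile the synopsis, section 5.1, the thrombocytopenia and eltrombopag dosing text of section 8.1.2, and Table 2. State which text governs at 200 k/µL or more in the eltrombopag-alone phase, and which governs restart after an interruption once the count has been above 50,000 for two weeks.
- Reconcile the starting-dose statements in section 5.1 and synopsis Arm B with those in synopsis Arm A, the synopsis dosing box, the Figure 1 footnote and section 8.1.2, including whether the group is Asian or East Asian.
- Correct the table references: Table 4 in the synopsis and Table 3 in section 8.1.2 should match the caption of the eltrombopag guidelines, now Table 2. Check that Figures 1, 4 and 5 agree with the reconciled text.

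The cost is a protocol wording amendment and a memo to sites, with no added visits or patients.
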